12.4.3. Definition of Cardiovascular Events

Cardiovascular Events (CV) Definition:
Investigators will be required to fill out the specific CV event page of the CRF for the following AEs and SAEs:

- Myocardial infarction/unstable angina
- Congestive heart failure
- Arrhythmias
- Valvulopathy
- Pulmonary hypertension
- Cerebrovascular events/stroke and transient ischemic attack
- Peripheral arterial thromboembolism

- Deep venous thrombosis/pulmonary embolism
- Revascularization

12.4.4. Recording of Aes and SAEs

Aes and SAE Recording:

- When an AE/SAE occurs, it is the responsibility of the investigator to review all documentation (e.g., hospital progress notes, laboratory, and diagnostics reports) relative to the event.
- The investigator will then record all relevant information regarding an AE/SAE in the CRF
- It is **not** acceptable for the investigator to send photocopies of the subject's medical records to GSK in lieu of completion of the GSK, AE/SAE CRF page.
- There may be instances when copies of medical records for certain cases are requested by GSK. In this instance, all subject identifiers, with the exception of the subject number, will be blinded on the copies of the medical records prior to submission of to GSK.
- The investigator will attempt to establish a diagnosis of the event based on signs, symptoms, and/or other clinical information. In such cases, the diagnosis will be documented as the AE/SAE and not the individual signs/symptoms.

12.4.5. Evaluating Aes and SAEs

Assessment of Intensity

The investigator will make an assessment of intensity for each AE and SAE reported during the study and will assign it to one of the following categories:

- Mild: An event that is easily tolerated by the subject, causing minimal discomfort and not interfering with everyday activities.
- Moderate: An event that is sufficiently discomforting to interfere with normal everyday activities
- Severe: An event that prevents normal everyday activities. – an AE that is assessed as severe will not be confused with an SAE. Severity is a category utilized for rating the intensity of an event; and both Aes and SAEs can be assessed as severe.
- An event is defined as 'serious' when it meets at least one of the pre-defined outcomes as described in the definition of an SAE.

Assessment of Causality

- The investigator is obligated to assess the relationship between study treatment and the occurrence of each AE/SAE.
- A “reasonable possibility” is meant to convey that there are facts/evidence or arguments to suggest a causal relationship, rather than a relationship cannot be ruled out.
- The investigator will use clinical judgment to determine the relationship.
- Alternative causes, such as natural history of the underlying diseases, concomitant therapy, other risk factors, and the temporal relationship of the event to the study treatment will be considered and investigated.
- The investigator will also consult the Investigator Brochure (IB) and/or Product Information, for marketed products, in the determination of his/her assessment.
- For each AE/SAE the investigator **must** document in the medical notes that he/she has reviewed the AE/SAE and has provided an assessment of causality.
- There may be situations when an SAE has occurred and the investigator has minimal information to include in the initial report to GSK. However, **it is very important that the investigator always make an assessment of causality for every event prior to the initial transmission of the SAE data to GSK.**
- The investigator may change his/her opinion of causality in light of follow-up information, amending the SAE data collection tool accordingly.
- The causality assessment is one of the criteria used when determining regulatory reporting requirements.

Follow-up of AEs and SAEs

- The investigator is obligated to perform or arrange for the conduct of supplemental measurements and/or evaluations as may be indicated or as requested by GSK to elucidate as fully as possible the nature and/or causality of the AE or SAE.
- The investigator is obligated to assist. This may include additional laboratory tests or investigations, histopathological examinations or consultation with other health care professionals.
- If a subject dies during participation in the study or during a recognized follow-up period, the investigator will provide GSK with a copy of any post-mortem findings, including histopathology.
- New or updated information will be recorded in the originally completed CRF.
- The investigator will submit any updated SAE data to GSK within the designated reporting time frames.

12.4.6. Reporting of SAEs to GSK

SAE reporting to GSK via electronic data collection tool

• Primary mechanism for reporting SAEs to GSK will be the electronic data collection tool• If the electronic system is unavailable for greater than 24 hours, the site will use the paper SAE data collection tool and fax it to the Medical Monitor or the SAE coordinator.• Site will enter the serious adverse event data into the electronic system as soon as it becomes available.• After the study is completed at a given site, the electronic data collection tool (e.g., InForm system) will be taken off-line to prevent the entry of new data or changes to existing data.• If a site receives a report of a new SAE from a study subject or receives updated data on a previously reported SAE after the electronic data collection tool has been taken off-line, the site can report this information on a paper SAE form or to the Medical Monitor or the SAE coordinator by telephone.• Contacts for SAE receipt can be found at the beginning of this protocol on the Sponsor/Medical Monitor Contact Information page.

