Serious adverse events (SAEs) reported from ongoing clinical studies with mepolizumab are reviewed daily by the project Medical Monitor. Additionally, regular, systematic reviews of emerging safety data from all clinical studies are conducted by an in-house multi-disciplinary Safety Review Team (SRT) which provides a central and dedicated forum for review of emerging data which could impact subject safety. The SRT, which includes the project Medical Monitor, other physicians assigned to the project, clinical scientists and a statistician, review blinded and unblinded (i.e., from open-label trials) safety data from ongoing clinical studies with mepolizumab on a regular basis and conduct a comprehensive evaluation of the safety data upon completion of each study. Moreover, an integrated analysis of safety across the program is completed annually when additional safety data are available from completed studies. A re-assessment of benefit risk and the current Developmental Core Safety Information (DCSI) is completed at each SRT meeting subsequent to review of new data. Additionally, an Independent

Data Monitoring Committee (IDMC) will be utilized until completion of the lead study MEA115921; their primary focus will be the monitoring of cardiovascular safety and all cause mortality.

Furthermore, GSK has a standard and comprehensive process for the reporting and management of Sentinel Events. A sentinel event is an SAE that is not necessarily drug-related, but that has been associated historically with adverse reactions for other drugs, and is therefore worthy of heightened pharmacovigilance. Sentinel Events include acquired long QT syndrome, agranulocytosis, anaphylactic and anaphylactoid reactions, hepatotoxicity, renal failure, seizures, and Stevens Johnson syndrome/toxic epidermal necrolysis. Subsequent to the reporting of a sentinel event, the Medical Monitor promptly notifies the SRT and the GSK Global Safety Board and leads a thorough and comprehensive follow-up of the sentinel event with collection of all relevant data.

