7.3.1.1. Time period and Frequency for collecting AE and SAE information

- AEs and SAEs will be collected from administration of the first dose of mepolizumab and will continue indefinitely, see minimum schedule of assessments, Time and Events Table (Section 7.1)
- Any SAEs assessed as related to study participation (e.g., protocol-mandated procedures, invasive tests, or change in existing therapy) or related to a GSK product

will be recorded from the time a subject consents to participate in the study up to and including any follow-up contact.

- All SAEs will be recorded and reported to GSK within 24 hours, as indicated in Appendix 4. The treating physician is not obligated to actively seek Aes or SAEs in former study subjects. However, if the investigator learns of any SAE, including a death, at any time after a subject has discontinued mepolizumab treatment under the LAP, and he/she considers the event reasonably related to the study treatment or study participation, the investigator must promptly notify GSK.

NOTE: The method of recording, evaluating and assessing causality of Aes and SAEs plus procedures for completing and transmitting SAE reports to GSK are provided in Appendix 4

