9. STATISTICAL CONSIDERATIONS AND DATA ANALYSES

No statistical analysis will be conducted for this study. Reported data will be summarized.

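### The outage rule in Protocol 12.4.6 can run past the 24-hour SAE deadline in 7.3.1.1 and gives no route that secures it

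*Protocol*

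**What the plan says.** The deadline stands in Protocol 7.3.1.1: "All SAEs will be recorded and reported to GSK within 24 hours, as indicated in Appendix 4". It has no exception for a system failure and does not say from what moment the 24 hours count.

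The procedure stands in Appendix 4, Section 12.4.6:

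- Normal route: "Primary mechanism for reporting SAEs to GSK will be the electronic data collection tool".
- Outage: "If the electronic system is unavailable for greater than 24 hours, the site will use the paper SAE data collection tool", which is then faxed to the Medical Monitor or the SAE coordinator.
- Catching up: "Site will enter the serious adverse event data into the electronic system as soon as it becomes available". No hour limit is attached.
- After the tool is closed at study completion: "the site can report this information on a paper SAE form or to the Medical Monitor or the SAE coordinator by telephone". This is the only place in 12.4.6 that names the telephone.

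Section 12.4.5, on follow-up, adds "The investigator will submit any updated SAE data to GSK within the designated reporting time frames", but Appendix 4 lists no such time frames. The only mention of 24 hours anywhere in Appendix 4 is the outage tolerance.

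**The concern.** The downtime a site may let pass before paper becomes mandatory is longer than the whole reporting window. A site that looks up the 24-hour rule where 7.3.1.1 sends it finds a 24-hour figure there, but it is a waiting period and not a deadline.

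What is at stake is the speed of the first report of a serious event. Section 4.1 says "Serious adverse events (SAEs) reported from ongoing clinical studies with mepolizumab are reviewed daily by the project Medical Monitor". Section 4.4.1 lists that daily monitoring as a mitigation for systemic reactions, cardiovascular effects, infections and malignancies, and for immunogenicity by cross-reference. Daily review cannot cover an event that has not been sent. Section 7.3.1.5 also ties prompt SAE notification to legal and ethical duties. Treatment may continue for years (to July 2022 in the UK), so some sites may well meet an outage, although the documents give no outage frequency.

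**Working it through.** The protocol states no figure to reproduce here, so this is a timeline check.

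**Inputs**

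- Deadline: 24 h (7.3.1.1). Start of clock not stated. *Assumption:* it starts when the site learns of the SAE (time 0). The protocol's pregnancy rule in 7.3.2 counts from learning of the event, which makes this a natural reading but does not settle it.
- Paper trigger: more than 24 h of downtime (12.4.6). Start of downtime not stated. *Assumption for the main case:* it counts from the true start of the outage.
- s = start of outage in hours relative to awareness. D = its duration in hours. The SAE has not been entered when the outage starts.
- The catching-up bullet is read as entry when the system returns.

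**Formulas**

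- Paper becomes due just after s + 24.
- Electronic entry becomes possible again at s + D.
- A site doing only what 12.4.6 requires reports at whichever comes first. It is late if that is after 24 h.

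**Results**

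| s | D | Report under 12.4.6 | Against 24 h |
|---|---|---|---|
| −20 | 60 | paper, just after −20 + 24 = 4 h | in time |
| −12 | 60 | paper, just after 12 h | in time |
| −1 | 60 | paper, just after 23 h | in time |
| 0 | 60 | paper, just after 24 h | late |
| +1 | 60 | paper, just after 25 h | late |
| +6 | 60 | paper, just after 30 h | late |
| +6 | 22 | paper never due; electronic at 6 + 22 = 28 h | late |
| +6 | 12 | electronic at 6 + 12 = 18 h | in time |

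Three things follow.

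1. If the outage had already run h hours at awareness (s = −h, h between 0 and 24), paper falls due 24 − h hours after awareness. For any h above 0 that is inside the deadline.
2. If the outage starts k hours after awareness (0 ≤ k < 24) and continues, paper falls due at k + 24 hours, so between 24 and just under 48 hours. The report is late whenever the outage lasts past hour 24, that is, D > 24 − k.
3. An outage shorter than 24 hours can cause a late report without ever triggering paper, as the 22-hour case shows.

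**Sensitivity to the second assumption.** If the site counts downtime from its own first failed attempt, p hours after awareness, paper falls due after p + 24 hours: 24 h for p = 0, 32 h for p = 8, 47 h for p = 23. On that count every case is late unless the system returns first, including outages that began before awareness.

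**The case against.** The strongest reply is that the two rules do not collide. The deadline in 7.3.1.1 is unconditional. Section 12.4.6 says when paper must be used and does not forbid using it sooner. A site that faxes the form at hour 10 of an outage satisfies both sections, and so does a site whose system comes back in time. This stands. A reader might infer that the two rules cannot both be met in an outage, or that following 12.4.6 always breaches the deadline. The documents support neither: the first ignores earlier use of paper, and the second fails for every outage already under way at awareness, if downtime is counted from its true start.

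A second reply is that other routes may exist. Section 12.4.6 refers sites to the sponsor contact page for SAE receipt. That page is not in the text available for this review, but the tables for Amendments 04 and 05 show that it names the Medical Monitor as SAE contact and has columns for daytime and after-hours telephone numbers. So one cannot say that no telephone route exists. One can say that 12.4.6 does not direct a site to it during an outage.

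A third reply concerns weight. Section 4.4.1 does not rank its mitigations and lists others, such as targeted CRF pages and observation after the first three doses. The Safety Review Team also meets regularly. This is fair, and it limits the consequence to a delay in individual first reports. The use of an IDMC only until the lead study completes has no bearing on how fast an SAE is sent.

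None of this removes the defect. That a careful site may act sooner than instructed does not cure an instruction that permits lateness.

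**Conclusion.** The concern holds in a limited form. Section 12.4.6 does not secure the deadline in 7.3.1.1, and a site doing exactly what it says can report late. On the assumption that the deadline runs from awareness, this happens when an outage starts at or after awareness, before entry, and is still running at hour 24. In the worst case paper is not due until just under 48 hours, about twice the limit. If downtime is counted from the site's own failed attempt, the range of late cases is wider. How often any of this would occur cannot be estimated from the documents.

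The consequence is for the timeliness of safety reporting. The protocol says of its analysis "No statistical analysis will be conducted for this study. Reported data will be summarized", and no endpoint, population or display in the SAP depends on the point.

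**What to change.** Reconcile 7.3.1.1 with 12.4.6:

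- Reword the outage bullet in 12.4.6: whenever the electronic system will not allow an SAE to be reported inside the 24-hour limit, the site sends the paper SAE form, or telephones, to the Medical Monitor or SAE coordinator within that limit, and enters the data when the system returns.
- State the 24-hour limit in 12.4.6, where 7.3.1.1 says it is to be found, and say when it starts. The time frames mentioned in 12.4.5 would then have something to refer to.

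With the trigger tied to the deadline, the start of downtime no longer needs defining. The cost is a short change to Appendix 4, a note to sites and a few more paper forms during outages. No analysis has to be altered.

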12.5. Appendix 5 – Country Specific Requirements

Amendments 01, 02 and 04 include a country-specific local amendment generated for the United Kingdom (UK).

The UK regulatory authority has requested the following clarifications highlighted in ***bold italics***.

Overall study design (Section 1: Protocol Synopsis for Study MEA115921, Overall Design, paragraph 6 and Section 4.1: Overall Design, paragraph 6):

UK only clarification: Eligible subjects can continue to receive mepolizumab under this LAP until ***June 2018*** or until the Sponsor discontinues development in EGPA or until the subject meets any of the withdrawal/stopping criteria.

Section 5.3: Withdrawal/Stopping Criteria, paragraph 2, bullet 5 and Section 5.4: Subject and Study Completion

UK only clarification: *Eligible subjects can continue to receive mepolizumab under this LAP until June 2018.*

12.6. Appendix 2 – Anaphylaxis Criteria

Hypersensitivity reactions will be monitored using the diagnostic criteria for anaphylaxis as outlined by the Joint NIAID/FAAN Second Symposium on Anaphylaxis [Sampson, 2006]. The criteria do not make a distinction based on underlying mechanism. These criteria are summarized as follows:

- 7) Acute onset of an illness (minutes to several hours) with involvement of the skin, mucosal tissue, or both (e.g., generalized hives, pruritus or flushing, swollen lips-tongue-uvula), and at least one of the following:
 - e) Respiratory compromise (e.g., dyspnea, wheeze-bronchospasm, stridor, reduced PEF, hypoxemia)
 - f) Reduced BP or associated symptoms of end-organ dysfunction (e.g., hypotonia [collapse], syncope, incontinence)
- 8) Two or more of the following that occur rapidly after exposure to a likely allergen for that patient (minutes to several hours):
 - i) Involvement of the skin-mucosal tissue (e.g., generalized hives, itch-flush, swollen lips-tongue-uvula)
 - j) Respiratory compromise (e.g., dyspnea, wheeze-bronchospasm, stridor, reduced PEF, hypoxemia)
 - k) Reduced BP or associated symptoms (e.g., hypotonia [collapse], syncope, incontinence)
 - l) Persistent gastrointestinal symptoms (e.g., crampy abdominal pain, vomiting)
- 9) Reduced BP after exposure to known allergen for that patient (minutes to several hours):
 - e) Infants and children: low systolic BP (age specific) or greater than 30% decrease in systolic BP
 - f) Adults: systolic BP of less than 90 mm Hg or greater than 30% decrease from that person's baseline

Appendix 3 – Acceptable Birth Control:

UK only clarification: ***True** abstinence from penile-vaginal intercourse **when this is in line with the preferred and usual lifestyle of the subject.***

Overall study design (Section 1: Protocol Synopsis for Study MEA115921, Overall Design, paragraph 6 and Section 4.1: Overall Design, paragraph 6):

UK only Clarification: Eligible subjects can continue to receive mepolizumab under this LAP until June 2021 or until the Sponsor discontinues development in EGPA or until the subject meets any of the withdrawal/stopping criteria.

Section 5.3: Withdrawal/Stopping Criteria, paragraph 2, bullet 5 and Section 5.4: Subject and Study Completion

UK only clarification: *Eligible subjects can continue to receive mepolizumab under this LAP until June 2021.*

UK only clarification: *Eligible subjects can continue to receive mepolizumab under this LAP until July 2022.*

12.7. Appendix 6 – Protocol Changes

12.6.1 Protocol Amendment 01

This amendment applies to sites in the UK only.

List of protocol changes:

Text which has been added to the protocol is highlighted in ***bold, italic*** typeface. Text which has been deleted from the protocol is indicated by ~~strike-through~~ format.

Change	Section, Text affected, and Rationale
1.	
Section 1: Protocol Synopsis for Study MEA115921, Overall Design, paragraph 6.
 
Section 4.1: Overall Design, paragraph 6.
 
Added:
 
United Kingdom (UK) only clarification: Eligible subjects can continue to receive mepolizumab under this LAP until June 2018 unless mepolizumab is commercially licensed for the treatment of EGPA in the relevant country prior to this date or until the Sponsor discontinues development in EGPA or until the subject meets any of the withdrawal/stopping criteria.
 
Rationale: Clarification requested by the UK regulatory authority.

2.	
Appendix 1 – Abbreviations and Trademarks
 
Added:
 
UK: United Kingdom

3.	
Appendix 3– Acceptable Birth Control; bullet 3
 
Modified:
 
UK only: True abstinence from penile-vaginal intercourse when this is in line with the preferred and usual lifestyle of the subject.
 
Rationale: Clarification requested by the UK regulatory authority.

4.	
Appendix 5 – Country Specific Requirements:
 
Changed from:
 
No country specific requirements exist.

Change Section, Text affected, and Rationale***Changed to:***

Amendment 01 includes a country-specific local amendment generated for the United Kingdom (UK).

The UK regulatory authority has requested the following clarifications highlighted in ***bold italics***.

Overall study design (Section 1: Protocol Synopsis for Study MEA115921, Overall Design, paragraph 6 and Section 4.1: Overall Design, paragraph 6):

UK only clarification: Eligible subjects can continue to receive mepolizumab under this LAP until ***June 2018 unless*** mepolizumab is commercially licensed for the treatment of EGPA in the relevant country ***prior to this date*** or until the Sponsor discontinues development in EGPA or until the subject meets any of the withdrawal/stopping criteria.

Appendix 3 – Acceptable Birth Control:

UK only clarification: ***True*** abstinence from penile-vaginal intercourse ***when this is in line with the preferred and usual lifestyle of the subject.***

12.6.2 Protocol Amendment 02

This amendment applies to sites in the UK only.

List of protocol changes:

Text which has been added to the protocol is highlighted in ***bold, italic*** typeface. Text which has been deleted from the protocol is indicated by ~~strike-through~~ format.

Change	Section, Text affected, and Rationale
1.	
Section 1: Protocol Synopsis for Study MEA115921, Overall Design, paragraph 6.
 
Section 4.1: Overall Design, paragraph 6:
 
Deleted:
 
United Kingdom (UK) only clarification: Eligible subjects can continue to receive mepolizumab under this LAP until June 2018 unless mepolizumab is commercially licensed for the treatment of EGPA in the relevant country prior to this date or until the Sponsor discontinues development in EGPA or until the subject meets any of the withdrawal/stopping criteria.
 
Rationale: Clarification requested by the UK regulatory authority.

2.	
Section 5.3: Withdrawal/Stopping Criteria, paragraph 2, bullet 5.
 
Section 5.4: Subject and Study Completion, paragraph 1
 
Added:
 
UK only clarification: Eligible subjects can continue to receive mepolizumab under this LAP until June 2018.
 
Rationale: Clarification requested by the UK regulatory authority.

3.	
Appendix 5 – Country Specific Requirements:
 
Added and deleted:
 
Amendments 01 and 02 includes a country-specific local amendment generated for the United Kingdom (UK).
 
UK only clarification: Eligible subjects can continue to receive mepolizumab under this LAP until June 2018 unless mepolizumab is commercially licensed for the treatment of EGPA in the relevant country prior to this date or until the Sponsor discontinues development in EGPA or until the subject meets any of the withdrawal/stopping criteria.

Change Section, Text affected, and Rationale

***Section 5.3: Withdrawal/Stopping Criteria, paragraph 2, bullet 5 and
Section 5.4: Subject and Study Completion***

Added:

UK only clarification: *Eligible subjects can continue to receive mepolizumab under this LAP until June 2018.*

Rationale: Clarification requested by the UK regulatory authority.

12.6.3 Protocol Amendment 03

This amendment applies to all countries.

List of protocol changes:

Text which has been added to the protocol is highlighted in ***bold, italic*** typeface. Text which has been deleted from the protocol is indicated by ~~strike-through~~ format.

Change	Section, Text affected, and Rationale
1.	
TITLE PAGE: Authors
 
Deleted/Added:
 
PPD
 
Rationale:
 
Change in team personnel.

2.	
MEDICAL MONITOR/SPONSOR INFORMATION PAGE
 
Deleted:
 
Secondary Medical Monitor: PPD BSc MBChB FRCA PhD
 
Rationale:
 
[name] has left GSK.

3.	
Section 5.2: Exclusion Criteria, Exclusion #6: Other Biological Therapy, Section 6.5.1 Permitted Medications and Non-Drug Therapies and Section 6.5.2: Prohibited Medications and Non-Drug Therapies
 
Added:
 
Section 5.2: Exclusion Criteria, Exclusion #6
 
5. Subject is receiving treatment with another biological therapy such as a monoclonal antibody therapy or IV immunoglobulin therapy without prior agreement from the GSK Medical Monitor.
 
Section 6.5.1 Permitted Medications and Non-Drug Therapies
 
Concomitant therapy with another biological therapy (e.g., monoclonal antibodies or IV immunoglobulin therapy) should be discussed with the GSK Medical Monitor prior to beginning therapy. If allowed, therapy

Change Section, Text affected, and Rationale

should not be administered at the same time as the mepolizumab injection(s) and physicians should take measures to separate administration of another biological therapy as long as possible from administration of mepolizumab.

Deleted:

Section 6.5.2: Prohibited Medications and Non-Drug Therapies

~~Section 6.5.2 Prohibited Medications and Non-Drug Therapies~~

~~Concomitant administration of other biological therapies such as monoclonal antibodies or IV immunoglobulin therapy.~~

Rationale: It is recognised that there may be occasions when physicians may want to administer another biological therapy for a condition other than EGPA while a patient is being treated with mepolizumab. The GSK Medical Monitor will need to assess each drug's safety profile and any potential safety concern with the combination and thus as a precaution, use of another biologic therapy in addition to mepolizumab will require approval from the GSK Medical Monitor. In addition, the treating physician will be asked to take measures to separate administration of another biological therapy as long as possible from administration of mepolizumab.

12.6.4 Protocol Amendment 04

Amendment changes 1 and 2 apply to all countries. Amendment change 3 and 4 apply to sites in the UK only.

List of protocol changes:

Text which has been added to the protocol is highlighted in ***bold, italic*** typeface.

Change	Section, Text affected, and Rationale																													
1.	Section 9 Statistical Considerations and Data Analyses																													
	
Added:
 <h3>9.1 Interim Analysis</h3> 
When required, an interim analysis will be performed in order to provide open-label safety data to inform the risk-benefit assessment of mepolizumab in EGPA.
																													
2.	MEDICAL MONITOR/SPONSOR INFORMATION PAGE																													
	
  
 Role	Name	Day Time Phone Number and email address	After-hours Phone/Cell/ Pager Number	Fax Number	Site Address	
   
 Primary Medical Monitor	PPD			n/a	GSK Upper Providence, PA, USA	
 
 Secondary Medical Monitor				n/a	GSK Research Triangle Park, NC, USA	
 
 SAE contact information	Medical monitor as above					
  
						Role	Name	Day Time Phone Number and email address	After-hours Phone/Cell/ Pager Number	Fax Number	Site Address	Primary Medical Monitor	PPD			n/a	GSK Upper Providence, PA, USA	Secondary Medical Monitor				n/a	GSK Research Triangle Park, NC, USA	SAE contact information	Medical monitor as above				
Role	Name	Day Time Phone Number and email address	After-hours Phone/Cell/ Pager Number	Fax Number	Site Address																									
Primary Medical Monitor	PPD			n/a	GSK Upper Providence, PA, USA																									
Secondary Medical Monitor				n/a	GSK Research Triangle Park, NC, USA																									
SAE contact information	Medical monitor as above																													
3.	Section 1: Protocol Synopsis for Study MEA115921, Overall Design,																													

Change	Section, Text affected, and Rationale
	
paragraph 6.
 
Section 4.1: Overall Design, paragraph 6.
 
Added:
 
UK only Clarification: Eligible subjects can continue to receive mepolizumab under this LAP until June 2021 or until the Sponsor discontinues development in EGPA or until the subject meets any of the withdrawal/stopping criteria.
 
Rationale: Clarification requested by the UK regulatory authority.

4.	
Section 5.3: Withdrawal/Stopping Criteria, paragraph 2, bullet 5.
 
Section 5.4: Subject and Study Completion, paragraph 1
 
Added:
 
UK only clarification: Eligible subjects can continue to receive mepolizumab under this LAP until June 2021.
 
Rationale: Clarification requested by the UK regulatory authority.

12.7.5. Protocol Amendment 05

Amendment changes 1 and 2 apply to all countries. Amendment change 3, 4 and 5 apply to sites in the UK only.

List of protocol changes:

TEXT WHICH HAS BEEN ADDED TO THE PROTOCOL IS HIGHLIGHTED IN *BOLD*, *ITALIC* TYPEFACE

Change	Section, Text affected, and Rationale					
